6.9.2 Immune-related Adverse Events

Immune-related AEs are specific to immunotherapies and vary by organ system. Immune-related AEs are considered AESIs for both M7824 and pembrolizumab.

In general, the spectrum of irAEs are similar for both M7824 and pembrolizumab.

The following irAEs are important identified risks for M7824.

- Immune-related pneumonitis
- Immune-related hepatitis
- Immune-related colitis
- Immune-related nephritis and renal dysfunction
- Immune-related endocrinopathies (thyroid disorders, adrenal insufficiency, type 1 diabetes mellitus, pituitary disorders)
- Immune-related rash
- Other immune-related events (myositis, myocarditis, encephalitis)

The following irAEs are important potential risks for M7824:

-
- Guillain-Barré syndrome
 - Uveitis
 - Pancreatitis
 - Myasthenia gravis/myasthenic syndrome

The Medical Monitor may be involved as needed for Follow-up. Details of the diagnostic work-up will be requested by the study team.

The recommendations for irAE management, are guided by the joint American Society of Clinical Oncology (ASCO) Clinical Practice Guidelines (Brahmer, 2018) and National Comprehensive Cancer Network (NCCN) (NCCN Guidelines®), listed in Appendix 5. Of note, official guidance is also available from Merck Sharp & Dohme for management and drug discontinuation for certain irAEs in the pembrolizumab FDA label (Keytruda USPI). These irAEs include: pneumonitis, colitis, hepatitis, endocrinopathies (including hypophysitis, thyroid disorders, type 1 diabetes mellitus), and nephritis. This pembrolizumab-specific guidance is covered in the ASCO/NCCN guidelines; however, resources from Merck & Company for participants who develop these irAEs while on the pembrolizumab treatment arm are to be considered as well.

General management by NCI-CTCAE v5.0 grading, as per ASCO, is listed below:

- Grade 1: study treatment should be continued with close monitoring, with the exception of some neurologic, hematologic, and cardiac toxicities.
- Grade 2: study treatment may be suspended for most Grade 2 toxicities, with consideration of resuming when symptoms revert to Grade 1 or less. Corticosteroids may be administered (initial dose of 0.5 to 1 mg/kg/d of prednisone or equivalent).
- Grade 3: study treatment is generally suspended and the high-dose corticosteroids (prednisone 1 to 2 mg/kg/d or methylprednisolone 1 to 2 mg/kg/d) treatment should be initiated. Corticosteroids should be tapered over the course of at least 4 to 6 weeks. Some refractory cases may require infliximab or other immunosuppressive therapy.
- Grade 4: in general, permanent discontinuation of study treatment is recommended, with the exception of endocrinopathies that have been controlled by hormone replacement.

Permanent treatment discontinuation is required in case of immune-related Grade 4 rash/inflammatory dermatitis, nephritis, autoimmune hemolytic anemia, hemolytic uremic syndrome, aplastic anemia, immune thrombocytopenia and acquired thrombotic thrombocytopenic purpura (TTP).

For Grade 4 immune-related lymphopenia, permanent treatment discontinuation will be required, if lymphopenia is considered immune-related in nature, no clear alternative explanation exists for the event, and Grade 4 lymphopenia does not resolve within 14 days. Permanent treatment discontinuation is not required when the AE is manifest by a single laboratory value out of normal range without any clinical correlates. In this case, treatment should be held until the etiology is determined. If the event is not considered immune-related and resolves to Grade ≤ 1 restarting treatment may be considered.

For additional organ/system specific management guidelines, review ASCO guideline tables in [Appendix 5](#).

Recommended guidance and management for specific irAEs are provided in the current NCCN guideline available at <http://www.nccn.org>.

6.9.3 TGF β Inhibition Mediated Skin Reactions

TGF β inhibition mediated skin reactions, including hyperkeratosis, KA and/or cutaneous squamous cell carcinomas (cSCC), are important identified risks for M7824 and considered as AESI. Cases of KA and cSCC have also been reported for patients under treatment with other checkpoint inhibitors as well (Freites-Martinez, 2017; Bednarek, 2018). The distribution of lesions tends to be in sun-exposed areas. Skin assessments will be performed for all participants per the SoA (see [Table 1](#)).

Management guidelines for potential TGF β inhibition mediated skin reactions are:

1. Discontinuation or interruption is not required in most cases. Continuation of treatment should be evaluated by the Investigator.
2. Emollients may continue to be used.
3. Diagnostic and treatment plan should be developed in collaboration between Investigator and dermatologist. In general, treatment of TGF β mediated skin lesions such as hyperkeratosis, KA and cSCC should be based on local guidelines/SoC. Lesion evaluation should include excision biopsy of one representative lesion to confirm diagnosis.
4. Treatment and Follow-up for KA and cSCC will depend on number and localization of lesions.
 - For single lesions: Full excision may be recommended.
 - In case of multiple lesions or location not suitable for full excision, other treatment options may be offered by the dermatologist, such as:
 - Mohs surgery, cryotherapy, or other standard treatment options depending on the pathology.
 - Use of retinoids, if recommended by dermatologist, may be considered after discussion with Medical Monitor.
5. Close clinical Follow-up for re-evaluation, resolution, or potential recurrence should be implemented.
6. Spontaneous resolution of KA lesions without surgical intervention has been observed, typically occurring within weeks after discontinuing M7824.
7. The number and localization of lesions, diagnosis (including histopathological diagnosis), treatment, and outcome should be appropriately documented in the eCRF.

Consult with study Medical Monitor, as needed, for management of TGF β -mediated skin reactions.

6.9.4 Anemia

Anemia is an AESI and an important identified risk for M7824. Notably, there are many reasons for anemia in patients with advanced cancer, therefore a thorough investigation of new anemia cases of unspecified etiology is requested.

For new anemia events items queried may include, but are not limited to, detailed relevant past medical and treatment history, bruising tendency, history of blood transfusions and/or dependency, and a request for an updated eCRF including details such as concomitant medications, all laboratory data, updated dosing information and, recent tumor evaluation scans.

General guidance for anemia management and evaluation:

- Participants must enter the study with hemoglobin values at least 9 g/dL; Routine blood test parameters are specified in [Table 16](#).
- All relevant hematologic testing for treatment-related anemias should be done prior to blood transfusion, if clinically feasible.
- If a participant experiences significant anemia (e.g., < 8 g/dL), then the amount of blood to be drawn may be reduced by not taking blood at selected time points for pharmacodynamic CCI and CCI. The decision to reduce the time points for these CCI will be taken by the Investigator in consultation with the Medical Monitor. This will be documented. Blood will continue to be taken as scheduled for safety analyses, PK, and anti-drug antibodies (ADAs).
- Transfusion should be performed at the discretion of the Investigator, based on clinical assessment and considered when participant experiences significant anemia. attempt should be made to initiate work-up (as specified below) for cause of anemia prior to transfusion if clinically feasible to not confound this work-up. Guidance for evaluation of suspected anemias is provided in [Table 9](#).
- Discuss further management with Medical Monitor for clinically significant treatment-related anemias.

Table 9 Evaluation Guidance of Suspected Anemia Adverse Events

Basic Anemia Evaluation	

 1. CBC with emphasis on red cell indices (e.g., Hgb, hematocrit, MCV, RDW, MCH, MCHC, reticulocytes counts). 2. If indicated and at clinical discretion, the following should be considered: 
 a. Iron studies (TIBC, Ferritin, Fe) b. Serum Folate and Vit B12 values c. Coagulation factors (PT, PTT, INR) d. Fecal occult blood testing e. Urinalysis f. Hormone panel: TSH, Erythropoietin g. Peripheral blood smear for cell morphological assessment 	
Further Recommendation Based on Suspected Etiology (in Addition to Baseline Anemia Testing)	
Suspected hemolysis:	Bilirubin level, LDH, Coombs test, fibrinogen, haptoglobin, d-Dimer Consider Hematology consultation.
Suspected bleeding:	Consider imaging/interventional radiology consultation as indicated Consider endoscopy, as clinically indicated. Consider imaging, as clinically indicated.
Suspected aplastic anemia:	Hematology consultation. Consider bone marrow aspiration/morphologic evaluation.

CBC=complete blood count, Fe=Iron, Hgb=hemoglobin, INR=international normalized ratio, LDH=lactate dehydrogenase, MCH=Mean Corpuscular Haemoglobin, MCHC=Mean Corpuscular Haemoglobin Concentration, MCV=mean corpuscular volume, PT = prothrombin time, PTT=partial thromboplastin time, RDW= Red Blood Cell Distribution Width, TIBC=total iron binding capacity, and TSH=thyroid-stimulating hormone.
	

6.9.5 Bleeding Events

Bleeding AEs are AESIs and considered important identified risk for M7824 (refer to the Investigator’s Brochure).

6.9.5.1 Mucosal/Non-tumor Bleeding

Participants treated with M7824 were commonly reported with mild to moderate mucosal AEs such as epistaxis, hemoptysis, gingival bleeding and hematuria. In general, these reactions resolve without discontinuation of treatment.

- If a Grade 2 treatment-related TEAE improves to Grade \leq 1 or completely resolves by the day before the next infusion, M7824 may be continued
- If a Grade 2 treatment-related non-tumor bleeding does not improve to Grade \leq 1 or completely resolve by the day before the next infusion, but it is manageable and/or not clinically relevant, the Medical Monitor should be consulted to assess if it is clinically reasonable to administer the following infusion.
- For Grade 3 non-tumor bleeding, study treatment must be permanently discontinued unless an alternative explanation can be identified (such as concomitant use of antithrombotic agents,

traumatic event, etc). In case of alternative explanations for the Grade 3 bleeding event, study treatment should be held until the event recovers to Grade ≤ 1 .

- For Grade 4 non-tumor bleeding, treatment must be permanently discontinued if no alternative explanation is identified.

6.9.5.2 Tumor Bleeding

Participants treated with M7824 were reported in lower frequencies, with Grade ≥ 3 hemorrhages including tumor bleeding.

For Grade ≥ 2 tumor bleeding, study treatment must be held until the event recovers to Grade ≤ 1 . Treatment should be permanently discontinued if the Investigator considers the participant to be at risk for additional severe bleeding.

7 Discontinuation of Study Intervention and Participant Discontinuation/Withdrawal

7.1 Discontinuation of Study Intervention

Participants will be withdrawn from treatment for any of the following reasons:

- A participant may withdraw from the study at any time, at his/her own request (i.e, withdrawal of consent), and without giving a reason.
- Occurrence of an exclusion criterion, which is clinically relevant and affects the participant's safety, if discontinuation is considered necessary by the Investigator and/or Sponsor.
- The participant may be withdrawn at any time at the discretion of the Investigator for safety, behavioral, compliance, or administrative reasons.
- Confirmed PD per RECIST 1.1 with the exception that participants receiving treatment may continue past PD if the participant's ECOG PS has remained stable, and if in the opinion of the Investigator, the participant will benefit from continued treatment. See Section 4.1.
- Some ADRs require withdrawal from treatment. See Section 6.8.2 for additional details.
- Drug must not be given to a known pregnant participant.
- Use of a nonpermitted concomitant drug (without approval by the Sponsor and the Medical Responsible), as defined in Section 6.5.2, where the predefined consequence is withdrawal from the study intervention.

Please note: one reinitiating course of treatment at the same dose and schedule and treatment duration up to 24 months is allowed at the discretion of the Investigator and agreement of the Study Medical Responsible for:

- Participants who are experiencing SD, a PR, or CR on either study arm at the time of discontinuation, and then subsequently develop disease progression after stopping therapy, but prior to the end of the study.

OR

- Participants who are discontinued due to an AE that are subsequently well managed or resolved after stopping therapy, but prior to the end of the study.
- Participants meeting the definition of confirmed PD while on-treatment based on RECIST 1.1. (Participants who experience PD may continue treatment with study drugs if the Investigator believes the participant will experience clinical benefit from the treatment and there is no unacceptable toxicity resulting from the treatment. Such participants will be withdrawn from the treatment if any other criteria for withdrawal are met or if alternative treatment options are available and indicated).

A discussion between the Investigator and Sponsor's Medical Responsible should take place. The Investigator will need to confirm that the benefit of reinitiating treatment outweighs any risk involved, such as that which led to initial treatment discontinuation. For participants with only SD at time of discontinuation, the Investigator should confirm no other reasonable treatment options are available. In addition, to be eligible for reinitiation, the participant must not withdraw consent, and should be followed with regular evaluation scans as specified in Section 1.3 (Schedule of Activities). No cross-over is allowed. Prior to reinitiation of the study intervention, malignant disease must be radiologically restaged within 28 days of dosing to assess all known sites disease. Relevant safety laboratory results must be available and verified prior to reinitiating treatment. Participants who reinitiate treatment will stay on study and will be treated and monitored according to Section 1.3 (Schedule of Activities). A discussion with the study team is warranted to determine if repeating PK/CCl testing is indicated when restarting treatment. A rollover protocol may accommodate M7824 participants if available at the time of reinitiation.

Section 1.3 (Schedule of Activities) specifies the data to collect at study intervention discontinuation and follow-up, and any additional evaluations that need to be completed.

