6.8.2 Adverse Drug Reactions Requiring Treatment Discontinuation

Adverse drug reactions are defined in this study as any AEs related to study intervention assessed by the Investigator and/or Sponsor. Serious adverse reactions are ADRs which are assessed as serious. Any questions or concerns with regards to management and/or follow-up of ADRs should be discussed with the Medical Monitor.

Immune-related AEs, IRRs including hypersensitivity, anemia, TGF β -mediated skin reactions, and bleeding events are managed and followed-up in their respective sections as indicated below. Permanent Treatment discontinuation may be recommended, so the relevant section must be reviewed:

- For management and guidance of suspected irAEs, see Section 6.9.2.
- For infusion-related reactions and hypersensitivity reactions guidance, see Section 6.9.1.
- For anemia guidance, see Section 6.9.4.
- For guidance and management for potentially TGF β mediated skin AEs, see Section 6.9.3
- For guidance and management of bleeding events, see Section 6.9.5.

General guidance:

- In any case, if ≥ 2 doses are missed due to AE, the Medical Monitor should be consulted.
- Inability to reduce corticosteroid dose to 10 mg or less of prednisone or equivalent per day within 12 weeks is an indication for permanent treatment **discontinuation** (except for use of steroids as hormone substitution).
- Persistent Grade 2 or 3 adverse reactions (excluding endocrinopathies controlled with hormone replacement therapy) that do not recover to Grade ≤ 1 within 12 weeks after last dose of study intervention is an indication for permanent treatment discontinuation.

Grade 4 ADRs:

- Participants with Any Grade 4 ADRs require permanent treatment discontinuation except:
 - a. Isolated laboratory values out of normal range that do not have any clinical correlation. Discuss with Medical Monitor regarding work-up, management, and treatment continuation versus hold versus discontinuation for isolated Grade 4 laboratory abnormalities.
 - b. Endocrinopathies controlled with hormone replacement therapy.
 - c. If alternative explanation is identified for Grade 4 non-tumor bleeding.

See Section 6.9.2 for other suspected Grade 4 irAEs, as most require permanent treatment discontinuation.

Grade 3 ADRs:

1. Participants with any severe or Grade 3 treatment-related adverse reactions that recur should be permanently discontinued. Exceptions may be considered as follows after discussion with Medical Monitor:

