 - a. Transient (≤ 6 hours) Grade 3 flu-like symptoms or fever, which is controlled with medical management.
 - b. Transient (≤ 24 hours) Grade 3 fatigue, local reactions, headache, nausea, emesis that resolves to \leq Grade 1 or baseline.
 - c. Tumor flare phenomenon defined as local pain, irritation, or rash localized at sites of known or suspected tumor.
 - d. Grade 3 hemoglobin decrease (< 8.0 g/dL) that is clinically manageable with blood transfusions or erythroid growth factor.
 - e. Increases in ECOG PS ≥ 3 that resolves to ≤ 2 by Day 1 of the next infusion (i.e., infusions should not be given if the ECOG PS is ≥ 3 on the day of treatment and should be delayed until ECOG PS ≤ 2).
 - f. Keratoacanthomas and/or cSCC (see Section 6.9.3 for management).
 - g. Grade 3 non-tumor bleeding requiring intervention or hospitalization if alternative explanation can be identified (such as concomitant use of antithrombotic agents, traumatic event, etc).
2. See Section 6.9.2 for suspected Grade 3 irAEs as many require permanent treatment discontinuation, including pneumonitis and nephritis.
 - a. AST or ALT > 5 times ULN or total bilirubin greater than 3 times ULN must be permanently discontinued, *except* for participants with liver metastases (for example) who begin treatment with Grade 2 AST or ALT. These participants should be discontinued if AST or ALT increases by $\geq 50\%$ relative to baseline and lasts for at least 1 week.
3. Persistent Grade 3 adverse reactions (excluding endocrinopathies controlled with hormone replacement therapy) that do not recover to Grade ≤ 1 within 12 weeks after dose of treatment.

Grade 2 ADRs should be managed as follows:

- If a Grade 2 ADR resolves to Grade ≤ 1 by the day before the next infusion, treatment may continue.
- If a Grade 2 ADR does not resolve to Grade ≤ 1 by the day before the next infusion, but it is manageable and/or not clinically relevant, the Medical Monitor should be consulted to assess if clinically reasonable to administer the following infusion.

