6.9.1 Infusion-related Reactions Including Immediate Hypersensitivity

Infusion-related reactions, including hypersensitivity, are defined in this section. Infusion-related reactions are AESIs and identified risks for M7824.

Infusion-related reactions are defined as any signs or symptoms experienced by participants occurring during or within 1 day of study intervention administration. An assessment for possible IRR should be triggered based upon the development of specific symptoms within 24 hours of an infusion.

These possible IRRs are identified based on a list of Medical Dictionary for Regulatory Activities (MedDRA) preferred terms and criteria based on the timely relationship to an infusion. Events are divided into reactions versus signs and symptoms:

- Infusion-related reactions should be considered when onset is on the day of infusion (during or after the infusion) or the day after the infusion (irrespective of resolution date) for infusion-related reaction, drug hypersensitivity, anaphylactic reaction, hypersensitivity, and Type 1 hypersensitivity.
- Signs and symptoms of IRRs and hypersensitivity/allergic reactions should be considered when onset is on the day of infusion (during or after the infusion) and resolved completely with the end date within 2 days after onset of (but not limited to) pyrexia, chills, flushing, hypotension, dyspnea, wheezing, back pain, abdominal pain, and urticaria.

Management of Infusion-Related Reactions

Current experience in more than 700 study participants revealed that IRRs to M7824 occur seldomly and are generally mild to moderate in severity. Therefore, administration of a premedication is generally not required.

If an investigator deems necessary to administer a premedication to a particular participant, an antihistamine (e.g. 25 to 50 mg diphenhydramine) and paracetamol (acetaminophen, 500 to 650 mg iv or equivalent oral dose) 30 to 60 minutes prior to M7824 infusion is recommended. Premedication should be administered for subsequent M7824 doses based upon clinical judgment and presence/severity of prior infusion reactions. This regimen may be modified based on local

treatment standards and guidelines as appropriate, provided it does not include systemic corticosteroids.

Table 8 Treatment Modification for Symptoms of Infusion-related Reactions

NCI-CTCAE v5.0 Grade	Treatment Modification

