Grade 1 – mild Mild transient reaction; infusion interruption not indicated; intervention not indicated.	Increased monitoring of vital signs as medically indicated, presuming these participants are deemed medically stable.
Grade 2 – moderate Therapy or infusion interruption indicated but if responds promptly to symptomatic treatment (for example, antihistamines, NSAIDs, narcotics, IV fluids); prophylactic medications indicated for ≤ 24 hours.	Stop M7824/ Pembrolizumab infusion. Increased monitoring of vital signs as medically indicated as participants are deemed medically stable by attending Investigator. If symptoms resolve quickly or decreased to Grade 1, resume infusion at 50% of original rate with close monitoring of any worsening otherwise dosing held until resolution of symptoms with mandated premedication for the next schedule. If worsens to Grade 3 or 4, follow treatment modification guidelines accordingly.
Grade 3 or Grade 4 – severe or life-threatening Grade 3: Prolonged (for example, not rapidly responsive to symptomatic medication and/or brief interruption of infusion); recurrence of symptoms following initial improvement; hospitalization indicated for clinical sequelae. Grade 4: Life-threatening consequences; urgent intervention indicated.	Stop the M7824/Pembrolizumab infusion immediately and disconnect infusion tubing from the participant with additional appropriate medical measures and close monitoring until deemed medically stable by attending Investigator. Hospitalization may be indicated. Participants will be permanently withdrawn immediately from M7824/ Pembrolizumab treatment and must not receive any further M7824/Pembrolizumab treatment
NCI-CTCAE = National Cancer Institute-Common Terminology Criteria for Adverse Event; NSAIDs = nonsteroidal anti-inflammatory drugs. For Grade 3 or 4 infusion-related reactions, M7824/Pembrolizumab discontinuation is mandated. For all types and grades of infusion reactions, details about drug physical constitution, method of preparation and infusion must be recorded.	

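### The Section 7.1 restart provision for resolved adverse events does not exclude events that other sections make a mandatory permanent stop

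*Protocol*

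**What the plan says.** A note in Protocol Section 7.1 states that "one reinitiating course of treatment at the same dose and schedule and treatment duration up to 24 months is allowed", subject to the Investigator's discretion and the Study Medical Responsible's agreement. One eligible group is "Participants who are discontinued due to an AE that are subsequently well managed or resolved after stopping therapy", provided the study has not ended. Among the conditions that follow, one concerns the original event: "The Investigator will need to confirm that the benefit of reinitiating treatment outweighs any risk involved, such as that which led to initial treatment discontinuation".

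The note comes directly after the list of reasons for withdrawal from treatment. That list covers drug reactions with the line "Some ADRs require withdrawal from treatment. See Section 6.8.2 for additional details".

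Other sections set absolute stops:

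- Section 6.8.2: "Participants with Any Grade 4 ADRs require permanent treatment discontinuation except" for three listed exceptions.
- Section 6.8.2, liver rule: "AST or ALT > 5 times ULN or total bilirubin greater than 3 times ULN must be permanently discontinued", with an exception for certain participants such as those with liver metastases.
- Table 8 in Section 6.9.1, for Grade 3 or 4 infusion-related reactions: the participant "must not receive any further M7824/Pembrolizumab treatment".
- Sections 6.9.2 and 6.9.5.1 and Appendix 5 add named immune-related events and unexplained non-tumor bleeding.

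**The concern.** A permanent stop means that the participant is not dosed again. Section 7.1 gives a route back to the same dose after an adverse-event discontinuation and does not say that the route closes when the stop was permanent. For a participant whose event has resolved, two parts of the protocol then give different answers, and no text says which prevails.

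At stake is re-exposure after a severe or life-threatening reaction. The adverse-event rows of the Schedule of Activities (Tables 1 and 3) send sites to Section 7.1 when study intervention is discontinued, so the restart note is text a site will meet in exactly this situation.

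**Working it through.** The plan gives no figure on this point and no arithmetic applies. The check sets the permission beside the prohibitions and looks for text that connects them.

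**Step 1: what restart requires.** Section 7.1 asks for:

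- an adverse-event discontinuation, with the event since managed or resolved;
- Investigator discretion and Medical Responsible agreement;
- a benefit-risk confirmation;
- consent still in place and continued scans;
- restaging within 28 days of dosing;
- verified safety laboratory results.

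None of these concerns the grade of the event, its type, or whether the stop was permanent.

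**Step 2: which stops are mandatory.**

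| Event | Where the stop is imposed | Excluded from restart in 7.1? |
|---|---|---|
| Grade 3-4 infusion-related reaction | Table 8 | No |
| Grade 4 adverse drug reaction, outside three exceptions | 6.8.2 | No |
| AST/ALT > 5x ULN or bilirubin > 3x ULN, outside the liver exception | 6.8.2 | No |
| Grade 3 or higher immune-related pneumonitis or nephritis | 6.8.2; Appendix 5, Tables A3 and A6 | No |
| Named Grade 4 immune-related events | 6.9.2; Appendix 5 introduction | No |
| Grade 3-4 non-tumor bleeding with no alternative explanation | 6.9.5.1 | No |

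The rows overlap. Most named Grade 4 immune-related events, for instance, are also Grade 4 drug reactions. The table lists places where an exclusion is missing; it is not a tally of distinct rules.

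**Step 3: is there a link?** The withdrawal list in 7.1 points to 6.8.2. Section 6.8.2 points to 6.9.1 through 6.9.5, and 6.9.2 points on to Appendix 5. This chain tells a site when to stop. Nothing in it says whether the restart note is available afterwards. Section 8 forbids waivers and exemptions, but a restart taken under 7.1 would be one the protocol itself provides for, so that rule does not settle precedence.

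**Step 4: one case in full.** Section 6.9.1 identifies the signs-and-symptoms type of infusion reaction partly by the event having "resolved completely with the end date within 2 days after onset". A Grade 3 or 4 event of this type therefore meets the 7.1 condition of having resolved, while Table 8 forbids any further dose. This follows from the definitions and says nothing about how often it happens. Table 8 describes Grade 3 as prolonged, recurring or needing hospital care, so the fast-resolving subset may be small.

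**Step 5: does the bullet have another use?** Yes. Temporary interruptions are mostly described as holding or suspending treatment (6.9.2, 6.9.5.2), which places permanent discontinuations within the bullet's wording. Some discontinuations are not permanent, however: Appendix 5, Table A8 stops treatment for Grade 3 aplastic anemia only until it improves to Grade 1, and 7.1 lets the Investigator withdraw a participant for safety. The bullet should be limited, not deleted.

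**The case against.** The strongest reply is that this is a missing cross-reference. The stops are worded as permanent; the restart bullet speaks only of discontinuation. A general permission does not displace a specific prohibition, and Table 8 is as clear a prohibition as a protocol can contain. Section 6.8.2 tells the reader to review the event-specific section, Section 8 forbids waivers, and two parties must agree before any restart. The benefit-risk sentence serves every restart route and makes good sense for non-permanent stops, so it does not show that permanent stops were meant to be weighed.

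Most of this stands. It makes the safe reading the natural one and keeps the practical risk low. It does not supply the missing statement: none of these provisions conditions the restart permission, and the one sentence in 7.1 about the original toxicity asks for a weighing.

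A reader might go further and infer that the protocol authorizes re-dosing after a life-threatening reaction, or that participants were re-exposed in this way. The documents support neither. The SAP plans to count and list participants with reinitiated treatment (Section 10.1), but that is a planned output and records no restart after a permanent stop.

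**Conclusion.** Section 7.1 is wrong as written: a stated permission literally covers events for which other sections forbid further dosing. The severity is minor. The conclusion rests on the absence of any exclusion or precedence statement, which is certain from the text, and on the judgment that re-exposure after such events should not depend on inference.

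No size is claimed. The number of participants affected cannot be derived, and a count of affected rules would depend on how overlaps and degrees of obligation are handled. There is no effect on alpha or power.

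Practical exposure is limited further because the sponsor discontinued the study (SAP Section 6.6). The SAP version that added that section is dated 22 April 2021; Protocol Version 4.0, dated 22 June 2021, still carries the bullet. The wording was therefore current two months later. That does not show that any participant with a permanent stop was a candidate for restart.

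**What to change.** Add to the adverse-event bullet in Section 7.1 that reinitiation is not permitted after:

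- a Grade 3-4 infusion-related reaction (Table 8);
- a Grade 4 adverse drug reaction outside the exceptions listed in 6.8.2;
- AST/ALT > 5x ULN or bilirubin > 3x ULN outside the 6.8.2 liver-metastasis exception;
- Grade 3 or higher immune-related pneumonitis or nephritis (6.8.2, Appendix 5);
- the Grade 4 immune-related events named in 6.9.2 and Appendix 5 (lymphopenia only under the conditions stated there);
- Grade 3-4 non-tumor bleeding without an alternative explanation (6.9.5.1).

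Notify sites of the change. Naming the events is better than a general reference to whatever 6.8.2 requires, because 6.8.2 also holds softer rules: the 12-week rules on steroid taper and persistent reactions, and the rule on recurrent Grade 3 reactions. Those stay under Medical Responsible review. The bullet remains available for discontinuations that were not permanent.

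The cost is one clause in an amendment and a site letter, with no new procedures or data. The only downside is loss of rechallenge discretion, which the listed sections already withhold.
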